2.1.5 Other endpoints

Other endpoints listed below are defined using same definitions and rules as for LDL-C, when applicable (see Section 2.1.3) and include:

- The absolute change in HbA_{1c} (%) from baseline to Week 24 in the double-blind period, as well as change from baseline to Week 68 and Week 104 in the OL period. PCSA criteria for HbA_{1c} will be also used (see Appendix A).
- The proportion of patients with 2 consecutives results, spaced out by at least 21 days, of LDL-C <50 mg/dL (<1.30 mmol/L), LDL-C <25 mg/dL (<0.65 mmol/L), LDL-C <15 mg/dL(0.39 mmol/L) during each treatment period (double-blind or open-label) and the time to the first LDL-C <50 mg/dL (<25 mg/dL, <15 mg/dL respectively) for these patients within the relevant treatment period.
- Cardiac function: CPK-MB and cardiac troponin (at Visit 4 [Week 0 / Day 1] and Visit 7 [Week 24]/or early termination) and in case of any clinically relevant cardiovascular effect observed in patients.
- The percent change in hs-CRP from baseline to Week 24 in the double-blind period. Hs-CRP values greater or equal to 10 mg/L will be excluded from analyses in a second approach, since these are suggestive of concurrent infections (1). PCSA (potentially

clinically significant abnormalities) criteria for hs-CRP will be also used (see Appendix A).

• Urine test at Visit 4 (Week 0 / Day 1) and Visit 7 (Week 24)/or early termination. Macroscopy will be performed at the central laboratory. If abnormal, then a standard microscope assessment will be conducted.

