 - If Not statin intolerant: [Subject treated with maximal dose of statin he can tolerate due to adverse event (AE) at higher dose [Yes, No]].
 - If Yes, AE(s) encountered at higher doses: [Skeletal muscle related events, Liver function test abnormalities, Co-morbid conditions such as impaired glucose tolerance/impaired fasting glucose, Other].
 - If No, reason of no statin intensification: [Regional practice or local guideline, Patient/parent's refusal, Other].
- Subjects, age of 8 to less than 10 years, have had other available interventions to lower calculated LDL-C, but these have been insufficient [Yes, No, NA].
- Type of lipid-modifying therapy ever taken: Statin, fibrates, bile acid sequestrant, cholesterol absorption inhibitor, nicotinic acid and derivates, omega 3 fatty acids ≥1000 mg/day) as reported in the "History of Hyperlipoproteinemia" e-CRF page.
- Background LMT at randomization, as reported in the dedicated prior & concomitant medications e-CRF pages.
 - Any statin
 - Atorvastatin daily dose in mg (<10, 10, 20, 40, 80, Other),
 - Rosuvastatin daily dose in mg (<5, 5, 10, 20, 40, Other),
 - Simvastatin daily dose in mg (<10, 10, 20, 40, >40, Other),
 - Pravastatin daily dose in mg (<10, 10, 20, 40, >40, Other),
 - Lovastatin daily dose in mg (<10, 10, 20, 40, >40, Other),
 - Fluvastatin daily dose in mg (<20, 20, 40, 80, >80, Other),
 - Pitavastatin (at any dose)

- Any LMT other than statins:
 - Ezetimibe,
 - Any other LMT other than nutraceuticals (by chemical class and drug name). This includes fenofibrate and other non-Statin LMT eg, niacin.
 - Nutraceuticals (Omega 3 fatty acids (<1000mg/day), Phytosterols, Psyllium/plantago, Policosanol, Other nutraceuticals).

Other baseline characteristics

Other baseline characteristics include:

- Glycated haemoglobin A1c (HbA1c) (quantitative and qualitative variable: <5.7%, ≥5.7% to <6.5%, ≥6.5%), and efficacy lipid parameters (quantitative variables for all efficacy parameters and the following categorical variables) will be also summarized at baseline (see definition in Section 2.1.3):
- LDL-C: <130, ≥130 to <160, ≥160 to <190, ≥190 mg/dL (ie, <3.37, ≥3.37 to <4.14, ≥4.14 to <4.91, ≥4.91 mmol/L).
- HDL-C: <40, ≥ 40 mg/dL (ie, <1.04, ≥ 1.04 mmol/L).
- Non-HDL-C: <160, ≥160 to <190, ≥190 to <220, ≥220 mg/dL (ie, <4.14, ≥4.14 to <4.91, ≥4.91 to 5.69, ≥5.69 mmol/L).
- Fasting TGs: <150, ≥150 to <200, ≥200 mg/dL (ie, <1.7, ≥1.7 to <2.3, ≥2.3 mmol/L).

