 - Selected using a CMQ, based on the following 5 HLGTs: "deliria (including confusion)", "cognitive and attention disorders and disturbances", "dementia and amnestic conditions", "disturbances in thinking and perception", and "mental impairment disorders".
 - A second grouping of terms for neurocognitive events was defined based on Regulatory Agency request (see Table 9 for the list of terms).
- Symptomatic overdose of IMP selected using appropriate MedDRA codes and the tick boxes "Overdose of Alirocumab" and "Symptomatic Overdose" in the overdose adverse event form.
- Pregnancy (including male patient's partner) selected using eCRF tick box.

In addition, the following additional grouping of events will be provided:

- Hepatic disorder events using SMQ "Hepatic disorder".
- Diabetes mellitus or diabetic complications using 1/HLGT "diabetes complications" (including PTs pertaining to the secondary SOC included in the HLGT), 2/ the HLT "diabetes mellitus", 3/ the HLT "carbohydrate tolerance analyses (including diabetes)" excluding PTs "blood glucose decreased" and "glycosylated haemoglobin decreased" and 4/ from the HLT "hyperglycaemic conditions NEC" only the following PTs "hyperglycaemia", "hyperglycaemic unconsciousness" and "hyperglycaemic seizure".

• Cataract using HLT "Cataract conditions".

Of note, groupings are based on the version of MedDRA currently in effect at Sanofi at the time of this SAP version (Version 23.1) and may be updated if appropriate, based on a more recent version available at time of database lock.

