2.4.5 Analyses of safety data

No formal inferential testing will be performed for either study period. Summaries will be descriptive in nature. All summaries of safety results described below will be presented for each study period respectively, unless otherwise noted.

General common rules

All safety analyses will be performed on the safety population for the double-blind period and on the OL population for the OL period, as defined in Section 2.3.2 unless otherwise specified, using the following common rules:

- Safety data in patients who do not belong to the safety population (ie, exposed but not randomized) will be listed separately.
- The baseline value for both double-blind and OL periods is defined as the last available value obtained up to the date and time of the first double-blind IMP injection in EFC14643 study, except otherwise specified.
- PCSA values are defined as abnormal values considered medically important by the Sponsor according to predefined criteria/thresholds based on literature review and defined by the Sponsor for clinical laboratory tests and vital signs, PCSA in children [Appendix A] and PCSA in adults version dated May 2014 [Appendix B]). Considering that the threshold defined in the PCSA list for monocytes and basophils can be below the ULN, the following PCSA criteria will be used for the PCSA analysis of monocytes and basophils:
 - PCSA criterion for monocytes: >0.7 Giga/L or > ULN (if ULN ≥ 0.7 Giga/L)
 - PCSA criterion for basophils: >0.1 Giga/L or > ULN (if ULN \ge 0.1 Giga/L)
- PCSA criteria will determine which patients had at least 1 PCSA during the TEAE period, taking into account all evaluations performed during the TEAE period, including nonscheduled or repeated evaluations.
- The treatment-emergent PCSA denominator by group for a given parameter will be based on the number of patients assessed for that given parameter at least once during the TEAE period.
- All measurements, scheduled or unscheduled, fasting or not fasting, will be assigned to analysis windows defined in Section 2.5.4, Table 5 and Table 6 in order to provide an assessment for Week 4 to Week 104 time points.

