2.4.5.3 Analyses of laboratory variables

The summary statistics (including number, mean, median, Q1, Q3, SD, minimum and maximum) of all laboratory variables (central laboratory values and changes from baseline) will be calculated for each visit or study assessment (baseline, each post-baseline value of the treatment period, last on-treatment and worst on-treatment value). In addition, for some parameters of interest, mean changes from baseline with the corresponding SE could be plotted over time (at same time points). This section will be organized by biological function as specified in Section 2.1.4.3. For glucose, only fasting samples will be summarized.

The incidence of PCSAs (list provided in Appendix A and Appendix B), as well as ALT increase as defined as AESI, at any time during the TEAE period will be summarized by biological function irrespective of the baseline level and/or according to the following baseline status categories:

- Normal/missing
- Abnormal according to PCSA criterion or criteria

For laboratory parameters for which PCSA criterion is not defined, similar table(s) using the normal range could be provided.

For clinical laboratory parameters during the OL period, summary tables as described for the double-blind period above will be used with the exceptions of the analyses by visit (unless data warrants further investigation)

Drug-induced liver injury

The liver function tests, namely AST, ALT, ALP, and total bilirubin, are used to assess possible drug-induced liver toxicity. The proportion of patients with PCSA values or ALT increase as defined in the section grouping of adverse events (see Section 2.1.4.1) during TEAE period by baseline status will be displayed for each parameter.

An evaluation of drug-induced serious hepatotoxicity (eDISH) with the graph of distribution of peak values of ALT versus peak values of total bilirubin will also be presented using post-baseline values during TEAE period. Note that the ALT and total bilirubin values are presented on a logarithmic scale. The graph will be divided into 4 quadrants with a vertical line corresponding to 3 x ULN for ALT and a horizontal line corresponding to 2 x ULN for total bilirubin.

Listing of possible Hy's law cases identified by treatment group (ie, patients with any elevated ALT>3 x ULN, and associated with an increase in bilirubin >2 x ULN, concomitantly or not) with ALT, AST, ALP, total bilirubin, and if available direct and indirect bilirubin will be provided.

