2.4.6 Analyses of other endpoints

All analyses/summaries for other endpoints will be performed on the safety population for the double-blind period and on the OL population for the OL period.

All measurements, scheduled or unscheduled, fasting or not fasting, will be assigned to analysis windows defined in Section 2.5.4, Table 5 and Table 6 in order to provide an assessment for Week 4 to Week 104 time points.

HsCRP and HbA_{1c}

Hs-CRP and HbA_{1c} parameters will be summarized by analysis visit using number of available data, mean, SD, median, minimum, and maximum (for hs-CRP, Q1 and Q3 will be also provided) during the treatment period. The time profile of each parameter will be also plotted with the means and the corresponding SEs for HbA_{1c} and the medians with (Q1-Q3) for hs-CRP. The incidence of PCSA at any time during the TEAE period will be also summarized using descriptive statistics.

Patients with low LDL-C

Binary endpoints defined in Section 2.1.5 will be described using count and percentage. Kaplan-Meier curves will be provided for the "Time to" variables in the double-blind treatment period. Patient without event will be censored at the end of the treatment period. For the analysis of the time to the first of the two consecutive LDL-C as defined in Section 2.1.5, patients without postbaseline LDL-C result or with only one post-baseline LDL-C result will not be included.

Creatine phosphokinase-MB and cardiac troponin

Creatine phosphokinase-MB parameter will be summarized at Week 24 on the safety population using number of available data, mean, SD, median, Q1, Q3, minimum, and maximum. In addition, similar tables as for PCSA will be provided using the normal range. This table will summarize the number (%) of patients with value >ULN during the TEAE period irrespective of the baseline level and/or according to the following baseline status categories \leq ULN, >ULN.

Cardiac troponin at Week 24 will be summarized on the safety population according to the following categories:

- <LLOQ;
- \geq LLOQ.

Urinalysis

The proportion of patients with at least one finding of proteinuria, hematuria or an abnormality on urine microscopy during the TEAE period will be summarized using descriptive statistics.

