7 LIST OF APPENDICES

Appendix A:	Potentially clinically significant abnormalities for children
Appendix B:	Potentially clinically significant abnormalities for adults
Appendix C:	Detailed statistical methodology for pattern mixture model
Appendix D:	List of MedDRA terms for CMQs
Appendix E:	Z-score calculation formula for Cogstate Battery test
Appendix F:	Cogstate normative data
Appendix G:	Effect size calculation formula for Cogstate data
Appendix H:	Pediatric formula for eGFR and creatinine clearance

Appendix A Potentially clinically significant abnormalities for children CRITERIA for POTENTIALLY CLINICALLY SIGNIFICANT ABNORMALITIES For studies in children

Parameter	Age range	PCSA	Comments
ECG parameters			Ref.: Rijnbeek P.R. et al., Eur Heart J 2001; Davignon A. et al., Ped Cardiol 1979/1980; Semizel E.et al., Cardiol Young 2008; Mulberg AE et al. Pediatric Drug Development Concepts and applications. John Wiley & sons, Inc. 2009
HR	Birth/0 to 27 days old (Neonates)	≤90 bpm and decrease from baseline ≥20 bpm ≥190 bpm and increase from baseline ≥20 bpm	
	28 days/1 month to 23 months old (Infants)	≤80 bpm and decrease from baseline $≥$ 20 bpm $≥$ 175 bpm and increase from baseline $≥$ 20 bpm	-
	24 months/2 years to <6 years old (Children)	\leq 75 bpm and decrease from baseline \geq 20 bpm \geq 140 bpm and increase from baseline \geq 20 bpm	
	6 to <12 years old (Children)	\leq 50 bpm and decrease from baseline ≥20 bpm ≥120 bpm and increase from baseline ≥20 bpm	-
	12 to 16/18 years old (Adolescents)	\leq 50 bpm and decrease from baseline ≥20 bpm ≥120 bpm and increase from baseline ≥20 bpm	-
PR	Birth/0 to 27 days old (Neonates)	≥120 ms	
	28 days/1 month to 23 months old (Infants)	≥140 ms	
	24 months/2 years to <6 years old (Children)	≥160 ms	
	6 to <12 years old (Children)	≥170 ms	-
	12 to 16/18 years old (Adolescents)	≥180 ms	

Parameter	Age range	PCSA	Comments
QRS	Birth/0 to 27 days old (Neonates)	≥85 ms	
	28 days/1 month to 23 months old (Infants)	≥85 ms	_
	2 to <6 years old (Children)	≥95 ms	_
	6 to <12 years old (Children)	≥100 ms	_
	12 to 16/18 years old (Adolescents)	≥110 ms	_
QTc	Birth/0 to <12 years old	Absolute values (ms) Borderline: 431-450 ms	To be applied to QTcF
	(Neonates,	Prolonged*: >450 ms	*QTc prolonged and
	Infants, Children)	Additional: ≥500 ms	$\Delta QTc > 60 ms are the$
		AND	PCSA to be identified in individual subjects/patients listings.
		Increase from baseline	

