Calcium ionized	All age ranges	≤1.0 mmol/L or 4.0 mg/dL	CF = mg x 0.025 = mmol
		≥1.4 mmol/L or 5.6 mg/dL	Based on normal range: 4.0 to 5.1 mg/dL

Parameter	Age range	PCSA	Comments
Total Cholesterol	All age ranges	≥6.20 mmol/L or 240 mg/dL	CF = g x 2.58 = mmol Based on normal ranges: 45 to 182 mg/dL (1-3 years), 109 to 189 mg/dL (4-6 years), 126 to 191 mg/dL (Boys 6-9 years), 122 to 209 mg/dL (Girls 6-9 years), 130 to 204 mg/dL (Boys 10-14 years), 124-217 mg/dL (Girls 10-14 years), 114 to 198 mg/dL (Boys 15-19 years), 125 to 212 mg/dL (Girls 14-19 years)
Triglycerides	All age ranges	≥4.0 mmol/L or 350 mg/dL	After >12 hours of fast) $CF = g \times 1.14 = mmol$ Based on normal ranges: 30 to 86 mg/dL (Boys 0-5 years), 32 to 99 mg/dL (Girls 0-5 years), 31-108 mg/dL (Boys 6-11 years), 35 to 114 mg/dL (Girls 6-11 years), 36 to 138 mg/dL (Boys 12-15 years), 43 to 138 mg/dL (Girls 12-15 years), 40 to 163 mg/dL (Boys 16-19 years), 40-128 mg/dL (Girls 16-19 years)
Lipasemia	All age ranges	≥2 ULN	Based on normal ranges: 3 to32 U/L (1-18 years)
Amylasemia	All age ranges	≥2 ULN	Based on normal ranges: 10 to 30 U/L (NN), 10 to 45 U/L (1-18 years)
Glucose	All age ranges	Hypoglycaemia <2.7 mmol/L or 50 mg/dL	CF = g x 5.55 = mmol
		Hyperglycaemia >7 mmol/L or 120 mg/dL (fasted after >12 hours of fast); >10.0 mmol/L or 180 mg/dL (unfasted)	Based on normal ranges: 50 to 90 mg/dL (NN), 60 to 100 mg/dL (Child)
Albumin	All age ranges	≤25 g/L	

Parameter	Age range	PCSA	Comments
CRP	All age ranges	>2 ULN or >10 mg/L (if ULN not provided)	Based on normal ranges: <6 mg/L FDA Sept 2005.
Hematology			Common Terminology Criteria for Adverse Events v3.0 (CTCAE), 2006; Division of Microbiology and Infections Diseases Pediatric Toxicity Tables, 2007; Division of AIDS Table for Grading the Severity of Adult and Pediatric Adverse Events, 2004; Mulberg AE et al. Pediatric Drug Development Concepts and applications. John Wiley & sons, Inc. 2009; Family Practice Notebook, LLC, 2012; Tietz NW et al. Clinical Guide to Laboratory Testing, 3rd edition 1995
WBC	Birth/0 to 27 days old (Neonates)	<4.0 GIGA/L or 4 000/mm ³ >25.0 GIGA/L or 25 000/mm ³	To be used if no differential count available
	28 days/1 month to 23 months old (Infants)	<4.0 GIGA/L or 4 000/mm ³ >20.0 GIGA/L or 20 000/mm ³	Based on normal ranges: 9 000 to 30 000/mm ³ (birth), 9 400 to 38 000/mm ³ (0-1 day).

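### The SAP takes its HbA1c abnormality limit from a children's list that has none; its only HbA1c limit is the adult >8%, so values of 6.5–8.0% are not counted by the PCSA flag

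*SAP*

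**What the plan says.** HbA1c is one of the other endpoints in SAP section 2.1.5, as absolute change from baseline to Week 24 in the double-blind period and to Weeks 68 and 104 in the open-label period. The same bullet adds that "PCSA criteria for HbA_{1c} will be also used (see Appendix A"). Section 2.4.6, under its heading for hs-CRP and HbA1c, plans number, mean, SD, median, minimum and maximum by analysis visit, a plot of means, and a count of abnormalities: "The incidence of PCSA at any time during the TEAE period will be also summarized using descriptive statistics".

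Appendix A is titled "Potentially clinically significant abnormalities for children". Its chemistry section includes a glucose limit, "Hyperglycaemia >7 mmol/L or 120 mg/dL (fasted after >12 hours of fast"), but no HbA1c limit. Appendix B, for adults, gives HbA1c >8%. The general rule in section 2.4.5 names both lists, "PCSA in children [Appendix A] and PCSA in adults version dated May 2014 [Appendix B"], and does not assign patients or parameters to one or the other.

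Section 2.1.1 does categorise HbA1c, as a "quantitative and qualitative variable: <5.7%, ≥5.7% to <6.5%, ≥6.5"%, but only to describe patients at baseline.

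**The concern.** A planned safety table should have a limit that a programmer can find and a reader can interpret. Here the reference leads to a list with no such limit. If the programmer then turns to the only HbA1c limit in the SAP, patients aged 8 to 17 at entry are judged by an adult limit of >8%, and a rise from below 6.5% to anywhere from 6.5% to 8.0% is not counted.

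Two things follow. A table showing no patients above 8% could be read as evidence of no glycaemic change when it is silent about the band beneath. Also, Week 24 is the only post-baseline HbA1c visit with a placebo comparison. If the criterion is not settled before that table is produced, it may be chosen after the data have been seen.

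**Working it through.** The plan gives no figure to reproduce. The check compares the cross-references and then applies each possible limit to example values.

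**Step 1. Does the reference resolve?** Appendix A was read row by row. Clinical chemistry runs from ALT to CRP and contains no HbA1c entry. A row lost in text conversion is unlikely: in Appendix B HbA1c stands between glucose and albumin, while in Appendix A albumin follows glucose directly and the list runs on to its end mark. The matching reference for hs-CRP in section 2.1.5 does resolve, because Appendix A has a CRP row.

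**Step 2. Which list would apply instead?** Section 2.4.5 allows two readings and states neither.
- By parameter: Appendix B is used where Appendix A has no row.
- By age: Appendix B is for adults, for example patients enrolled at 17 who pass 18 during the 104 weeks. Patients under 18 would then have no HbA1c limit.

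**Step 3. What is flagged?** Example values against the section 2.1.1 baseline category and the two lists:

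| HbA1c (%) | Baseline category | Appendix A | Appendix B (>8%) |
|---|---|---|---|
| 5.6 | <5.7 | no criterion | no |
| 6.0 | 5.7 to <6.5 | no criterion | no |
| 6.5 | ≥6.5 | no criterion | no |
| 7.0 | ≥6.5 | no criterion | no |
| 7.5 | ≥6.5 | no criterion | no |
| 8.0 | ≥6.5 | no criterion | no |
| 8.1 | ≥6.5 | no criterion | yes |
| 9.0 | ≥6.5 | no criterion | yes |

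Under Appendix A as cited, no value is flagged, not even 9.0%. Under Appendix B, flagging starts above 8.0%. The band from 6.5% to 8.0% is unflagged on both readings.

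**Step 4. Do other planned outputs count the same patients?**
- The summary in 2.4.6 includes the maximum. That shows one extreme value, not the number of patients or where they started.
- Section 2.4.5.3 says: "For laboratory parameters for which PCSA criterion is not defined, similar table(s) using the normal range could be provided". This is optional. It sits in the section on laboratory variables, while HbA1c is analysed under 2.4.6, and 2.1.5 says that a PCSA criterion will be used.
- The adverse-event grouping in section 2.1.4.1, "Diabetes mellitus or diabetic complications using 1/HLGT" and further terms, needs a reported event. Protocol section 10.4.3 limits when a laboratory change is recorded as one (symptoms, treatment or consultation, effect on study drug, seriousness, or special-interest status). HbA1c is not on the special-interest list in section 10.4.1.3.
- The glucose limit concerns a different analyte and is itself unclear. It presumes a fast of more than 12 hours, while protocol section 10 asks for at least 8. Its two units also disagree: by the list's own factor, 120 mg/dL = 1.2 g/L × 5.55 = 6.66 mmol/L, not 7.

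**The case against.** The strongest reply is that this is a wrong appendix letter and nothing more. Section 2.4.5 adopts both lists and, in the same bullet, adjusts the limits for monocytes and basophils, which appear only in Appendix B. The SAP therefore already uses Appendix B where Appendix A has no row, and HbA1c >8% fits that pattern. This stands to a large extent. A reader might infer that the table cannot be produced; more probably it would be produced at >8%. But no rule is written down, and the stated reference is still wrong.

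The second reply is that, once the letter is corrected, what remains is a preference for a lower limit. The 5.7% and 6.5% cut-points describe baseline and are nowhere called safety flags, so leaving them out after baseline contradicts nothing. That also stands. The case for a 6.5% row is that it uses a boundary already in the SAP and costs almost nothing; it does not follow from the broken reference alone. A shift at 5.7% has less claim still.

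Third, a reader might infer that a child rising to 6.5–8.0% would go unseen altogether. The documents do not support that, since the outputs in step 4 could show such a value. The statement holds for the PCSA count only.

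**Conclusion.** The point holds as a drafting error in a planned safety table, with a modest consequence. The HbA1c criterion is referred to a list that lacks it. The only limit available is the adult >8%, and no rule says that it applies. Either way, the PCSA count omits every value from 6.5% to 8.0%, at Week 24 and at Weeks 68 and 104.

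A reader might go further and expect the table to be nearly empty whatever the drug does. Nothing in the documents supports this: they give no HbA1c distribution and no expected rate of crossing, and a rise past 8% would be counted if Appendix B is used. The planned enrolment of about 150 is the number followed, not the number affected. Fewer will have open-label values, since section 1.3 assumes 15% discontinuation.

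HbA1c is an other endpoint, its summaries are descriptive, and no primary, key secondary or alpha decision depends on it. The conclusion assumes that the Appendix A text is complete, which step 1 supports.

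**What to change.** Make these changes before the first database lock, which SAP section 4 places about 4 weeks after the common cut-off date:

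- **Section 2.1.5:** replace the Appendix A reference for HbA1c with the criterion that applies and its source. Which limit serves as the PCSA is for the sponsor to state.
- **Section 2.4.5:** add a sentence saying which list applies to which patients or parameters, so that 2.1.5, 2.4.5, 2.4.6 and Appendix B agree.
- **Section 2.4.6:** add to the HbA1c table, by treatment group and period, the number of patients with baseline HbA1c below 6.5% and any value of 6.5% or more in the TEAE period. The denominator is patients with baseline below 6.5% and at least one HbA1c value in that period. Keep >8% as a further row. A shift from below 5.7% to 5.7% or more is optional.
- **Footnote:** section 2.4.5 uses the pre-treatment baseline for both periods, so a patient who crosses in the double-blind period and stays above 6.5% will also appear in the open-label row.

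The cost is a few lines of SAP text and one more descriptive row or table. No new data are needed.
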